13.5 Quality of life questionnaire

Under each heading, please check the ONE box that best describes your health TODAY.

MOBILITY

- I have no problems in walking about
- I have slight problems in walking about
- I have moderate problems in walking about
- I have severe problems in walking about
- I am unable to walk about

SELF-CARE

- I have no problems washing or dressing myself
- I have slight problems washing or dressing myself
- I have moderate problems washing or dressing myself

I have severe problems washing or dressing myself

I am unable to wash or dress myself

USUAL ACTIVITIES (e.g. work, study, housework, family, or leisure activities)

I have no problems doing my usual activities

I have slight problems doing my usual activities

I have moderate problems doing my usual activities

I have severe problems doing my usual activities

I am unable to do my usual activities

PAIN/DISCOMFORT

I have no pain or discomfort

I have slight pain or discomfort

I have moderate pain or discomfort

I have severe pain or discomfort

I have extreme pain or discomfort

ANXIETY/DEPRESSION

I am not anxious or depressed

I am slightly anxious or depressed

I am moderately anxious or depressed

I am severely anxious or depressed

I am extremely anxious or depressed

PLEASE RATE YOUR OVERALL HEALTH TODAY

The scale is from 0 to 100, where 0 is the WORST health you can imagine and 100 is the BEST health you can imagine.

Worst Health

Best Health

13.6 Medical history

SECTION 1: DEMOGRAPHICS Age Gender Height (inches) Weight (pounds)

DEFINITIONS OF RACIAL CATEGORIES:

White:

A person having origins in any of the original peoples of Europe, North Africa, or the Middle East.

Black or African American:

A person having origins in any of the Black racial groups of Africa.

Asian:

A person having origins in any of the original peoples of the Far East, Southeast Asia, or the Indian subcontinent including, for example, Cambodia, China, India, Japan, Korea, Malaysia, Pakistan, the Philippine Islands, Thailand, and Vietnam.

American Indian or Alaska Native:

A person having origins in any of the original peoples of North and South America, including Central America, and who maintains tribal affiliation or community attachment.

Native Hawaiian or Other Pacific Islander:

A person having origins in any of the original peoples of Hawaii, Guam, Samoa, or other Pacific Islands.

Please choose all that apply.

Please indicate whether you are of Hispanic ethnicity.

DEFINITION:

Hispanic or Latino:

A person of Cuban, Mexican, Puerto Rican, South or Central American, or other Spanish culture or origin regardless of race.

SECTION 2: MEDICAL HISTORY

What year was your constipation diagnosed?
Have you ever had an obstruction (blockage) of your bowel?
Have you ever had a fistula (abnormal tube-like connection between two organs)?
Have you had a perforation (cut/hole) in your bowel?
Have you had a fissure (tear in the skin) or abscess (pocket of inflamed tissue filled with pus) around the anus?

SECTION 3: SURGICAL HISTORY

Have you had an appendectomy (removal of the appendix)? If yes, date of your appendectomy:

Have you had a cholecystectomy (removal of the gallbladder)? If yes, date of your cholecystectomy:

Have you had a bowel resection (removal of part of the bowel)? If yes, date of your bowel resection:

SECTION 4: SOCIAL HISTORY

Do you exercise? Type of exercise? Please choose all that apply. Aerobic Strength training Yoga/stretching

How would you describe your level of physical activity?

Inactive: Rare physical work or exercise Active: Moderate physical work or leisure activities, such as running, cycling, swimming, or aerobics, for less than 30 minutes per day and less than 3 days per week Very Active: Strenuous physical work or activities, such as running, cycling, swimming, or aerobics, for more than 30 minutes per day and at least 3 days per week Do you, or did you, drink alcohol? If yes, what type of alcohol do you drink? How many standard drinks do you have per week? 1 glass of wine = 1.5 standard drinks 1 bottle of beer = 1 standard drink 1 oz. hard liquor = 1 standard drink Do you, or did you ever, smoke? If yes, what year did you start? Did you quit? If yes, what year did you quit? On average, how many cigarettes do you, or did you, smoke per week? Do you "vape" (use e-cigarettes)? Are you exposed to secondhand smoke? Do you, or did you ever, smoke marijuana? If yes, what year did you start? Did you quit? If yes, what year did you quit? Do you use recreational drugs (not including marijuana)? If yes, what type of recreational drugs do you use? Have you ever used recreational drugs in the past? If yes, what type of recreational drugs did you use in the past? SECTION 5: ADDITIONAL MEDICAL HISTORY (For female subjects only.) Have you ever been pregnant? If yes, how many times have you been pregnant? Have you ever taken hormone replacement therapy? If yes, how many years have you been taking/did you use hormone replacement therapy? Do you take birth control pills? Are you menopausal? If yes, natural or surgical menopause? Are you pre-menopausal? Please choose all that apply. No

Yes, hot flashes Yes, night sweats Yes, vaginal dryness

Have you had a hysterectomy?

If yes, what type of operation did you have?

Uterus

Uterus + one ovary

Uterus + both ovaries

14. References

# 1. ABBREVIATIONS

Abbreviation	Description
AE	Adverse Event
ANCOVA	Analysis of Covariance
ATC	Anatomical Therapeutic Chemical
AUC	Area Under the Curve
BMI	Body Mass Index
BSFS	Bristol Stool Form Scale
CH 4	Methane
CO 2	Carbon dioxide
CSBM	Complete Spontaneous Bowel Movement
CRF	Case Report Form
EQ-5D-5L	A standardized measure of health status developed by the EuroQol group
ECG	Electrocardiogram
EOS	End Of Study
FAS	Full Analysis Set
$H_2$	Hydrogen
$H_2S$	Hydrogen sulfide
IBS	Irritable Bowel Syndrome
LOCF	Last Observation Carried Forward
MAST	Medically Associated Science and Technology
Max	Maximum
MedDRA	Medical Dictionary for Regulatory Activities
Min	Minimum
NRS	Numeric Rating Scale
PAC-SYM	Patient Assessment of Constipation – Symptom
PP	Per-Protocol
QTcF	QT Corrected with Fridericia's Formula
SAP	Statistical Analysis Plan
SD	Standard Deviation
SBM	Spontaneous Bowel Movement

Abbreviation	Description	
TEAE	Treatment Emergent Adverse Event	
WHO	World Health Organization	

## 2. PURPOSE

[figure not shown]
This Statistical Analysis Plan (SAP) is based on Protocol Version 3.0 (9 January, 2019) and it describes in detail the statistical methodology and the statistical analyses to be conducted for the above-mentioned protocol.

Results obtained from the analyses outlined in this document will become the basis of the final clinical study report for this protocol. The purpose of this plan is to provide specific instructions as to how each analysis will be conducted.

#### 2.1. STUDY DESIGN

Single-center, randomized, double-blind, placebo-controlled clinical trial comprising three periods:

- 1. Screening and Pre-treatment Period (up to 17 days prior to the first dose of the study drug),
- 2. Treatment Period comprising Randomization (Day 1) and 12 weeks of dosing (with clinic visits at Weeks 4, 8, and 12), and
- 3. End-of-Study contact between 24 and 48 hours after Week 12 for patients who complete the Treatment Period.

# 2.2. DETERMINATION OF SAMPLE SIZE

The sample size calculation is based on the following assumptions: the weekly CSBM change from baseline is 0.5 for the placebo group, and 1.5 for each active group, with common standard deviation of 1.5. Fifty subjects in each group will have 90% power for each SYN-010 group compared with the placebo by using the t-test with 2-sided alpha = 0.05.

# 2.3. RANDOMIZATION AND ADMINISTRATION OF STUDY DRUG

After successful completion of the Screening and Pre-treatment Period, eligible patients will be randomized in a 1:1:1 ratio to receive study drug (SYN-010 21 mg, SYN-010 42 mg, or placebo). Subjects will take SYN-010 or matching placebo orally once daily at bedtime for 12 weeks.

#### 3. ENDPOINTS

#### 3.1. PRIMARY EFFICACY ENDPOINT

The primary efficacy endpoint is the change from baseline in the weekly average number of complete spontaneous bowel movements [CSBMs] during the 12-week Treatment Period.

A CSBM is a spontaneous bowel movement [SBM] that is associated with a sense of complete evacuation. An SBM is a bowel movement that occurs in the absence of rescue medicine use or other laxative use (e.g. suppository or enema) on the calendar day of bowel movement or the calendar day before the bowel movement.

#### 3.2. SECONDARY EFFICACY ENDPOINTS

The secondary efficacy endpoints are defined as below:

- Proportion of overall responders during the 12-week Treatment Period (overall 12-week responders). An overall 12-week responder is defined as a subject with a weekly response in at least 50% of the weeks of treatment (6 of 12 weeks). A weekly response is defined as a decrease in the subject's weekly average score for worst abdominal pain in the past 24 hours of at least 30% compared to baseline and a stool frequency increase of 1 or more CSBMs per week compared with baseline.
- Proportion of overall stool frequency responders during the 12-week Treatment Period. An
  overall stool frequency responder is defined as a subject with a weekly stool frequency
  response in at least 50% of the weeks of treatment (6 of 12 weeks). A weekly stool
  frequency response is defined as a stool frequency increase of 1 or more CSBMs per week
  compared with baseline, with abdominal pain unchanged or improved compared with
  baseline.
- Proportion of overall abdominal pain intensity responders during the 12-week Treatment Period. An overall abdominal pain intensity responder is defined as a subject with a weekly abdominal pain intensity response in at least 50% of the weeks of treatment (6 of 12 weeks). A weekly abdominal pain intensity response is defined as a decrease in the subject's weekly average score for worst abdominal pain in the past 24 hours of at least 30% compared to baseline, with stool frequency unchanged or improved compared with baseline.
- Proportion of overall bloating responders during the 12-week Treatment Period. An overall bloating responder is defined as a patient with a weekly bloating response in at least 50% of the weeks of treatment (6 of 12 weeks). A weekly bloating response is defined as a weekly average bloating score of at least 30% improvement compared to baseline, with stool frequency unchanged or improved compared with baseline.
- Proportion of patients using rescue medication.

Additional secondary endpoints are changes from baseline. The change from baseline at Visit X is defined as Value at Visit X – Value at Baseline. The percent change from baseline is defined as (change from baseline)/baseline value. If the baseline value = 0 or missing, then the percent change from baseline will be missing.

• Change from baseline in weekly average score for worst abdominal pain at Weeks 1 through 12.

- Percent change from baseline in weekly average score for worst abdominal pain at Weeks 1 through 12.
- Change from baseline in weekly average number of CSBMs at Weeks 1 through 12.
- Change from baseline in weekly average number of SBMs at Weeks 1 through 12.
- Change from baseline in weekly average bloating score at Weeks 1 through 12.
- Change from baseline in weekly stool consistency score (BSFS) at Weeks 1 through 12.
- Proportions of overall abdominal pain intensity responders with different cutoff points for the % improvement from baseline in weekly average score for worst abdominal pain, i.e., ≥ 10%, 20%, 40%, 50%, 60%, and 70%.
- Proportions of overall stool frequency responders with different cutoff points for the improvements from baseline in the weekly number of CSBMs  $\geq 2, 3, 4, 5$ , and 6.
- Proportions of overall bloating responders with different cutoff points for the % improvement from baseline in weekly average bloating score, i.e. ≥ 10%, 20%, 40%, 50%, 60%, and 70%.

#### 3.3. EXPLORATORY EFFICACY ENDPOINT

Exploratory endpoints are listed as the following parameters:

- Proportion of subjects who have adequate relief of Irritable Bowel Syndrome (IBS) symptoms.
- Change from baseline for SYN-010 in patient reported outcomes (PRO) using validated questionnaires in the REDCap system.
  - o Change from baseline in weekly PAC-SYM scores.
  - o Change from baseline in weekly straining score.
  - o Assessment of Quality of Life measures using the EQ-5D-5L questionnaire.
- Change from baseline in the area-under-the-curve (AUC) of breath CH4 production, based on the 120-minute lactulose breath test.
- Change from baseline in breath CH4 production based on a single-point breath CH4 test.

#### 3.4. SAFETY ASSESSMENTS

Safety assessments will include the collection of AEs, ECG recordings, laboratory tests (clinical chemistry, hematology, lipid, cytokine, and creatine phosphokinase), physical examinations, urine and serum pregnancy tests (when applicable), and rescue medication use.

# 4. ANALYSIS POPULATIONS

#### 4.1. RANDOMIZED SUBJECT POPULATION

The randomized subject population will consist of all subjects who are randomized.

#### 4.2. FULL ANALYSIS SET

The Full Analysis Set (FAS) will consist of all randomized subjects who receive at least one dose of study drug. The full analysis set will be used for the efficacy and safety analyses. Efficacy analysis will be conducted according to the randomized treatment the subjects receive, and safety analysis will be conducted according to the actual treatment the subjects receive.

#### 4.3. PER PROTOCOL ANALYSIS SET

The Per Protocol (PP) analysis set will consist of all subjects in the full analysis set who do not have any major protocol deviations. The major protocol deviations will include the following, but not limited to:

- Did not meet important eligibility criteria
- Missed more than 20% of planned medication

The Per Protocol (PP) analysis set will be identified before unblinding the study, and will be used in a secondary analysis of the primary endpoint and selected secondary endpoints.

#### 4.4. PROTOCOL DEVIATIONS

Protocol deviations identified by site staff and study monitors will be documented before database lock.

# 5. EFFICACY ASSESSMENTS

# 5.1. DAILY DIARY, BREATH TESTS, AND OTHER QUESTIONNAIRES

Subjects will be provided an ID number and password-protected access to the REDCap website to complete the information contained in the REDCap system each day, assessing stool frequency, SBMs, CSBMs, and use of rescue medication or other laxative use; stool consistency using the Bristol Stool Chart; abdominal pain using the Numeric Rating Scale (0-10), straining, and bloating assessment using a Likert scale (0-4). Questionnaires will also be completed weekly for PAC-SYM and Adequate Relief question. EQ-5D-5L questionnaire will be completed in the REDCap system on Day 1 prior to study drug administration and at Week 12 or upon early termination.

Lactulose breath tests will be performed during the Screening Visit and 12-Week Visit. Subjects will be asked to undergo a 24-hour preparatory period just prior to the test. Subjects will maintain a bland diet during the first 12 hours and fast during the remaining 12 hours. A baseline breath test will be collected by exhaling into disposable collection bag with a volume of 750 mL. Following the baseline breath sample, subjects will consume 10 g lactulose dissolved in water. Subsequent breath samples will be collected every 15 minutes over the remainder of the 120-minute test. Breath samples will be analyzed for hydrogen, methane, carbon dioxide, and hydrogen sulfide levels immediately after collection via gas chromatograph.

Methane breath tests will be performed during the Randomization Visit and the 4- and 8-Week Visits. Subjects will exhale into a disposable collection bag with a volume of 750 mL. Breath samples will be analyzed immediately after collection via gas chromatograph.

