8.8 Prior and concomitant therapy

Any prior or concomitant therapy that the patient may be taking and may be necessary for the patient's welfare taken within two weeks prior to the start of the study and during the study must be recorded in the patient's source documentation and in the CRF (including start/stop dates, dose frequency, route of administration, and indication).

The patient may be on a stable, continuous regimen of fiber, or probiotics one month before the Screening Visit; however, he/she must maintain a stable dose regimen through Week 12. Additionally, certain drugs used for the treatment of IBS (e.g. low dose tricyclic antidepressants) may be allowed at the discretion of the Medical Monitor provided the patient remains on a stable dose for one month prior to the Screening Visit and throughout the study with the exception of tegaserod, lubiprostone, linaclotide, metoclopramide, prucalopride, domperidone, plecanatide, CandiBactin, Atrantil, Allimax/Allimed within 2 weeks prior to the Screening Visit or antibiotics within 2 months prior to the Screening Visit.

Rescue medication will be allowed for severe constipation (i.e. when symptoms become intolerable). For guidance purposes for this protocol, intolerable symptoms may be when a subject has not had a complete spontaneous bowel movement (CSBM) in the preceding three days with an abdominal pain score of \geq 6 on an 11-point (0-10) scale each day during that time period. However, intolerability is ultimately a subjective judgment, and principal investigators and their patients make the final decision regarding what is intolerable and requires use of the rescue medication. For the Randomization Visit only, rescue medication will not be allowed the day before, the day of, or the calendar day after the Randomization Visit. If rescue medication is taken during this time, it must be recorded as a protocol deviation and the subject should not be randomized. The use of protocol-specified rescue medication and non-protocol-specified laxatives will be recorded in the subject record.

Permitted rescue medications include bisacodyl, magnesium citrate, magnesium hydroxide, and lactulose. Dosage and frequency should be followed according to package insert on rescue medication and should not exceed recommended doses as approved by package insert.

9. Procedures and variables

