9.1 Schedule of assessments

Table 1: Schedule of assessments

X = required; O = only if directed by symptoms or reported AE; ET = early termination

Visit No.	1		2	3	4	5	EOS
Туре	Screen	Pre-treatment	Randomize				Call/Visit
Days	-17 to -14	-17 to -1	1	28	56	84 or ET	85
Window (Days)				±5	±5	±5	+1
Participant Information							
Informed Consent ¹	Х						
Inclusion/Exclusion ¹	Х						
IBS-C Criteria (ROME IV) ¹	Х						
Demographics ²	Х						
Medical History ³	Х		х				
Prior/Concomitant Medications	х		х	х	х	х	х
Diary compliance/ eligibility to randomize ⁴		х	х				
Physical							
Physical Exam ⁵	Х		Х	0	0	Х	0
Vital Signs ⁶	Х		Х	Х	Х	Х	0
12-Lead ECG ⁷	Х					Х	
Drug Dispensing							
Drug Dispensing			х	Х	Х		
Accountability/Returns				Х	Х	Х	
Adverse Events							
AEs			Х	Х	Х	Х	Х
Blood Samples							
Clinical Chemistry (CMP)	Х		Х	Х		Х	
Lipid Panel			Х			Х	
Cytokine Analysis			Х	Х		Х	
Hematology	Х					Х	
Serum Pregnancy ⁸	Х						
Creatine Kinase (CK)	Х			0	0	0	0
Urine Samples							

Urine Drug Screen	Х						
Urine Pregnancy ⁸			Х	Х	Х	Х	
Patient Reported							
Outcomes (REDCap)							
Diary Dispensing or	v					v	
Return ⁹	^					^	
Diary Compliance ¹⁰		Х	Х	Х	Х	Х	
EQ-5D-5L QoL			×			v	
Questionnaire ¹¹			^			^	
Stool Samples ¹²							
Bacteria (16S rRNA)			Х			Х	
Methanogens (qPCR)			Х			Х	
Breath Gases							
Lactulose breath test ¹³	Х					Х	
Single-point breath test			Х	Х	Х		

¹Informed consent, inclusion/exclusion criteria, and ROME IV may be reviewed and signed prior to Visit 1.

²Date of birth, gender, race/ethnicity.

³Patients will complete the information in the REDCap system during the Screening Period.

⁴Patients will be eligible for randomization if they fully respond to the PRO questions on at least 11 of 14 days.

⁵General examination, including head, ears, eyes, nose, throat, endocrine, cardiovascular, respiratory, abdomen, skin, neurological, extremities, and musculoskeletal features.

⁶Body weight, blood pressure (requires the patient to be semi-supine for at least 5 minutes prior to the test) height (Screening Visit only), radial pulse rate, respiratory rate, and temperature.

⁷12-lead ECG requires the participant to be supine for at least 5 minutes prior to the test.

⁸All female participants of child-bearing potential.

⁹Provide and train the patient to use the REDCap system with questionnaire.

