#### 6.2. BASELINE AND STUDY DAY DEFINITIONS

Baseline definition will vary upon the data/variables for summaries/analyses.

Table 1: Baseline Definitions

Data/Variables	Baseline Definition
Laboratory, vital signs, and ECG	The last non-missing value prior to the first dose of the study drug
Breath CH 4 AUC measurement	AUC of breath CH 4 measurements collected during lactulose breath test performed at Screening after an overnight fast
Singe-point breath CH 4 measurement	A single-point breath CH 4 measurement collected at Randomization after an overnight fast
Weekly average score for worst abdominal pain in the past 24 hours	(Sum of daily pain scores) / (number of days with pain score assessment during the 7 days prior to the first dose of study drug)
Stool frequency of CSBMs per week/Weekly average number of CSBMs	7 x (sum of daily number of CSBMs) / (number of days with CSBM assessment

	during the 7 days prior to the first dose of study drug)
Stool frequency of SBMs per week/Weekly average number of SBMs	7 x (sum of daily number of SBMs) / (number of days with SBM assessment during the 7 days prior to the first dose of study drug.
Weekly average of bloating score	Sum of daily bloating scores / (number of days with bloating score assessments during 7 days prior to the first dose of study drug)
Weekly average of straining score	Sum of daily straining scores / (number of days with straining score assessments during 7 days prior to the first dose of study drug)
Adequate Relief	The last non-missing value prior to the first dose of the study drug
Weekly stool consistency score (BSFS)	Sum of (i $\times$ number of type i stools) / total number of stools during 7 days prior to the first dose of study drug, where stool consistency i = 1, 2,7
EQ-5D-5L score	The last non-missing value prior to the first dose of the study drug

Study day will be defined as follows:

- The first dose of study drug is designated as Day 1.
- For visit days after Day 1, study day = visit date Day 1 date + 1.
- For visit days prior to Day 1, study day = visit date Day 1 date. Thus, study days for screening visit are negative numbers. There is no "Day 0".

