The analysis will be conducted based on the following imputation method: If a subject drops out of the study or otherwise does not report efficacy data for a particular treatment-period week, the subject will not be considered a responder for that week. The weekly response will not be considered a responder if there are more than 3 days with missing assessments during a week.

Two sensitivity analyses for the overall responders will be conducted: (1) missing data for the responders will be imputed as "responders"; (2) the overall responders are defined based on the LOCF for missing values of the weekly average score for worst abdominal pain and/or weekly average number of CSBMs.

Additional secondary endpoints are change from baseline. The change from baseline at Visit X is defined as Value at Visit X - V alue at Baseline. The percent change from baseline is defined as (change from baseline)/baseline value. If the baseline value = 0 or missing, then the percent change from baseline will be missing.

- Change from baseline in weekly average score for worst abdominal pain at Weeks 1 through 12. Weekly average score for worst abdominal pain = (sum of daily worst abdominal pain scores) / (number of days with worst abdominal pain score assessment for the specific week).
- Percent change from baseline in weekly average score for worst abdominal pain at Weeks 1 through 12. Percent change from baseline in weekly average score for worst abdominal pain = (the weekly average score for worst abdominal pain for the specific week the weekly average score for worst abdominal pain at baseline) / (the weekly average score for worst abdominal pain at baseline).
- Change from baseline in weekly average number of CSBMs at Weeks 1 through 12. Weekly average number of CSBMs = 7 x (sum of daily number of CSBMs) / (number of days with CSBM assessment) for the specific week.

- Change from baseline in weekly average number of SBMs at Weeks 1 through 12. Weekly average number of SBMs = 7 x (sum of daily number of SBMs) / (number of days with SBM assessment) for the specific week.
- Change from baseline in weekly average bloating score at Weeks 1 through 12. Weekly average bloating score = (sum of daily bloating scores / number of days with bloating score assessment) for a specific week.

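### When the Visit 5 lactulose test falls inside a diary week, no rule handles it, so that week's CSBM and SBM scores and the rescue-use count depend on how the patient answers the laxative question

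*SAP*

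**What the plan says.** **The test.** SAP 5.1: "Lactulose breath tests will be performed during the Screening Visit and 12-Week Visit". The preparation takes 24 hours: "Subjects will maintain a bland diet during the first 12 hours and fast during the remaining 12 hours". Then "subjects will consume 10 g lactulose dissolved in water". Protocol 9.3.10.1 describes the same procedure. The schedule in Protocol 9.1 places Screening on Day -17 to -14 and Visit 5 on Day 84 (±5 days) or at early termination.

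**Lactulose as a laxative.** Protocol 8.8: "Permitted rescue medications include bisacodyl, magnesium citrate, magnesium hydroxide, and lactulose". The daily questionnaire (Protocol 13.3) asks about laxative use that day and names lactulose under the rescue option. It makes no exception for the breath test.

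**The counting rule.** SAP 3.1: "An SBM is a bowel movement that occurs in the absence of rescue medicine use or other laxative use", and the rule covers laxative use on the day of the movement or the day before. A CSBM must first be an SBM. SAP 8.2.1 computes the weekly score as seven times the summed daily counts divided by the number of days assessed. A day whose movements are disqualified therefore counts as zero and not as missing.

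**Where the scores are used.** The diary baseline is taken "during the 7 days prior to the first dose of study drug" (SAP 6.2). SAP 8.2.1 lists "Change from baseline in weekly average number of CSBMs at Weeks 1 through 12", and similar weekly analyses of SBMs, pain, bloating and stool form. Rescue use is the fifth secondary endpoint in the fixed sequence, and SAP 9.7 counts protocol-specified rescue at any point after baseline. SAP 6.4 has no rule for breath-test days.

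**The concern.** The lactulose drink is a study procedure, but the plan's definitions cannot tell it from rescue use. The Screening test does not balance it, because that test lies outside the baseline week. A diary week containing the Visit 5 test is therefore recorded under different conditions from baseline, and the error can go either way:

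- If the patient answers yes to the laxative question, true spontaneous movements are struck out and the days still count in the denominator.
- If the patient answers no, movements caused by the lactulose can count as spontaneous.

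Pain, bloating, straining and stool form have no laxative exclusion at all, so they are used as recorded in both cases.

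The weekly Week 12 results and within-arm changes are exposed. So is the rescue-use endpoint: it closes the 42 mg sequence, and SAP 8.2.1 opens formal testing of the 21 mg secondary endpoints only if every 42 mg endpoint has succeeded.

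**Working it through.** **1. The plan's own figure.** SAP 2.2 gives gains of 0.5 and 1.5, SD 1.5, 50 per group, two-sided alpha 0.05. The difference is 1.5 − 0.5 = 1.0. The noncentral t distribution gives power 0.910 (normal approximation 0.915), so the stated 90% is reproduced.

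**2. Timing.** The documents do not define diary weeks by study day. Assume Week 12 is Days 78–84. A Screening test on any of Days -17 to -14, with the day before and the day after, touches 0 of the 7 baseline days. For Visit 5:

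| Test on | Week 12 days under lactulose (test day and next) | Also counting the preparation day |
|---|---|---|
| Day 79–83 | 2 | 3 |
| Day 84 | 1 | 2 |
| Day 85 | 0 | 1 |
| Day 86–89 | 0 | 0 |

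The two-day entries need diary entry to continue after the test.

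**3. Lactulose recorded: the Week 12 difference.** Assume movements are spread evenly over the week. Striking k of 7 days multiplies the expected count by (7 − k)/7.

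- k = 1, all patients: 1.0 × 6/7 = 0.857.
- k = 2, all patients: 1.0 × 5/7 = 0.714.
- If only a share r record it, equally in each arm, the difference is 1 − r·k/7. For r = 0.5 and k = 1 that is 1 − 0.5/7 = 0.929.

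With SD held at 1.5 and 50 per arm, nominal Week 12 power is 91%, 81% and 65% for k = 0, 1 and 2. A Poisson-gamma count simulation (assumed baseline of 1 CSBM per week, SD about 2.0, t-test on change) gave 70–71%, 62–64% and 52–54% over two runs.

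**4. Lactulose recorded: within-arm gains.** With baseline b and true gain g, the apparent gain for k = 1 is (6/7)(b + g) − b. The documents give no mean baseline, so b is an assumption:

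| b | Placebo (true 0.5) | Active (true 1.5) |
|---|---|---|
| 0.5 | 0.36 | 1.21 |
| 1 | 0.29 | 1.14 |
| 2 | 0.14 | 1.00 |

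**5. Lactulose not recorded.** The documents give no effect for 10 g. If it adds 0.5 to 2 CSBMs in Week 12 equally in all arms (assumption), each arm's Week 12 gain rises by that amount. Each 12-week mean rises by 0.5/12 = 0.04 to 2/12 = 0.17. The difference between arms stays at 1.0.

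**6. Primary endpoint, recorded case.** The 12-week difference becomes (11 + 6/7)/12 = 0.988 or (11 + 5/7)/12 = 0.976, with power 90.3% or 89.7%. The largest relative change is 2/84 = 2.4%.

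**7. Responder endpoints.** Week 12 decides overall response only in a patient with exactly 5 responding weeks among the other 11. With independent weekly response probabilities of 0.2 to 0.5 (assumption), that is 4% to 23% of patients. In the simulation, the share gaining at least 1 CSBM in Week 12 fell by 5–6 points (one day) or 10–13 points (two days). The rough product runs from 0.04 × 0.05 = 0.2% to 0.23 × 0.13 = 3%.

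**8. Rescue-use endpoint.** If a share r of each arm is counted as a rescue user because of the test alone, a true rate p becomes 1 − (1 − p)(1 − r), and the difference shrinks by the factor 1 − r. Illustration with assumed rates of 50% and 20% and r = 0.5: the rates become 75% and 60%, the difference falls from 30 to 15 points, and power with 50 per arm falls from 89% to 36%.

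**The case against.** The strongest reply is that this is a recording detail with little reach. Much of that stands.

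- A reader might infer that Week 12 is distorted in every completer. The schedule does not support this: with the ±5-day window, tests on Days 85–89 put no lactulose day in Week 12.
- The two-day case is a bound. Protocol 9.1 has the diary returned and last checked at Visit 5, so the following day may never be entered.
- A reader might infer a bias in favour of SYN-010. The arms are blinded and have the same test, so the procedure by itself creates no difference between them.
- The weekly continuous results lie outside the fixed sequence and carry nominal P-values, so Week 12 power is not power for a formal test.
- LOCF does not spread the problem in completers, because nothing follows Week 12. It could do so only after an early-termination test. Protocol 6.6 reports 4 of 53 patients withdrawn or terminated early.
- Fasting is not peculiar to Visit 5. SAP Table 1 describes an overnight fast at Randomization. The lactulose and the bland diet are what differ.
- Rescue is meant for severe constipation, so patients may not report a diagnostic drink as a laxative. Full recording is an extreme, and permitted rescue use can strike days in any week.

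What does not stand is that the gap is harmless. The diary question literally covers the drink and names lactulose, and the SBM rule and weekly formula then give an understated count. Neither document says otherwise.

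**Conclusion.** The concern holds for a diary week that contains the Visit 5 or early-termination test. At the nominal Day 84 visit, a recorded test lowers the planned Week 12 CSBM difference from 1.0 to about 0.86. The 0.71 figure is an upper bound on the damage. These values assume Week 12 is Days 78–84, evenly spread movements and recording by every patient. Partial recording gives a smaller loss, and non-recording pushes counts the other way by an amount the documents do not allow to be sized.

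The documents do not support reading this as a threat to the primary result. In the recorded case its treatment difference moves by at most 2.4%, and in the unrecorded case an equal shift in all arms leaves the difference unchanged. The effect on overall response is also small. The one formally sequenced endpoint that could move materially is rescue use. Its size depends wholly on how often test lactulose is recorded, and the 89% to 36% example only illustrates this with assumed rates.

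**What to change.** Before unblinding, amend the SAP as follows.

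1. In 6.4 and 8.2.1, remove the calendar day of the breath test and the next calendar day from both numerator and denominator of the weekly diary scores (CSBM, SBM, stool form, pain, bloating, straining). Apply this to early-termination tests too.
2. State that removed days do not count toward the limit of three missing days. Otherwise a patient with two or three other missing days could lose the week or become a non-responder because of the procedure. State also that removed days are not filled in by the 6.4 rule that treats an unanswered question as no bowel movement.
3. State that breath-test lactulose is not rescue or laxative use for the rescue-medication endpoint and for 9.7.
4. Add a Week 12 sensitivity analysis that also omits the preparation day.

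The cost is a few sentences and a flag on the breath-test date. Up to two diary days per patient are lost in that week, leaving five of seven if the others are complete. In the simulation, dropping the days restored the difference to about 1.0 and the gains to about 0.5 and 1.5, while that week's SD rose from 2.00 to 2.06–2.18. With two days dropped and not zeroed, power was 63% against 54%. The share gaining at least 1 CSBM was not restored, so that single-week proportion still needs cautious reading.
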